21.4.8. Indirect Ophthalmoscopy

Indirect ophthalmoscopy will be performed for each eye at each visit with pupil dilation.

Indirect ophthalmoscopy will be used to examine the retina at each study visit. Indirect ophthalmoscopy will be performed prior to and within 30 minutes after each DE-122 or anti-VEGF medication injection. Areas to be assessed include cup to disc ratio, retina, macula and choroid, and vitreous.

Cup/Disc Ratio

The cup/disc ratio will be determined by the examiner and recorded using two decimal places (e.g., 0.80).

Retina, Macula and Choroid

The retina, macula and choroid will be evaluated for the presence of any clinically significant abnormalities, and graded as either normal (within normal limits) or abnormal (clinically significant abnormality present). A description of any abnormalities will be noted.

Vitreous

The following National Eye Institute Grading Scheme will be used to measure vitreous haze and opacification ([Nussenblatt et al., 1985](#)).

Vitreous Haze Scale

Step	Description
(0)	Clear
(Trace or 0.5+)	Trace
(1+)	Few opacities, mild blurring
(2+)	Significant blurring but still visible
(3+)	Optic nerve visible, no vessels seen
(4+)	Dense opacity obscures the optic nerve head

21.4.9. Spectral Domain Optical Coherence Tomography

Spectralis, Cirrus or 3D OCT will be utilized to take optical images of both eyes at each study visit. The same machine must be used consistently throughout the study for any given subject.

21.4.10. Fundus Photography

Digital color fundus photography will be taken at Screening (Day -7 to Day -1), Visit 5 (Day 30±2), Visit 7 (Day 60±3) and Visit 8/Exit (Day 90±3) in both eyes. Required fields to be captured are:

- The optic disc, Field 1
- The macula, Field 2

21.4.11. Fluorescein Angiography

Fundus fluorescein angiography will be taken at Screening (Day -7 to Day -1), Visit 5 (Day 30±2), Visit 7 (Day 60±3) and Visit 8/Exit (Day 90±3) in both eyes. Required fields to be captured are:

- The optic disc, Field 1
- The macula, Field 2

21.4.12. Urine Pregnancy Test

A urine pregnancy test will be conducted at Visit 5 (Day 30±2) and Visit 7 (Day 60±3) for all women of childbearing potential. A female is considered of childbearing potential unless she is post-menopausal (at least 24 months since last menses occurred), has had her uterus and/or both ovaries removed, or has had a bilateral tubal ligation. To obtain the pregnancy test, the subject should follow instructions provided by the manufacturer of the urine pregnancy test kit.

21.4.13. Serum Pregnancy Test

A serum pregnancy test will be conducted at Screening (Day -7 to Day -1) and Visit 8/Exit (Day 90±3) for all women of childbearing potential. A female is considered of childbearing potential unless she is post-menopausal (at least 24 months since last menses occurred), has had her uterus and/or both ovaries removed, or has had a bilateral tubal ligation. To perform the pregnancy test, Human chorionic gonadotropin (hCG) will be contained into serum parameters that will be measured.

21.4.14. Hematology, Chemistry and Urinalysis

Approximately 10 mL of fasting blood and urine samples will be obtained at Screening (Day -7 to Day -1), Visit 3 (Day 8±1), Visit 5 (Day 30±2) and Visit 8/Exit (Day 90±3). The subjects will be asked to fast for a minimum of 8 hours prior to each blood and urine collection. Samples will be sent to a central laboratory for analysis.

Serum Chemistry, Hematology

The following is a list of the minimum parameters that will be measured. Other additional parameters may also be reported.

Chemistry	Hematology
Albumin	red blood cells (RBC)
Creatinine	white blood cells (WBC)
lactate dehydrogenase (LDH)	differential WBC
glucose	platelets (PLT)
calcium	hemoglobin (HGB)
potassium	hematocrit (HCT)
sodium	mean corpuscular volume (MCV)
cholesterol (total, HDL and LDL)	mean corpuscular hemoglobin (MCH)
triglycerides	mean corpuscular hemoglobin conc. (MCHC)
urea nitrogen	
bilirubin (total, direct, indirect)	
alkaline phosphatase (ALP)	
alanine aminotransferase (ALT)	
aspartate aminotransferase (AST)	
gamma glutamyl transferase (GGT)	
Human chorionic gonadotropin (hCG)*	

Prior to enrolling a subject, the Clinical Investigator will indicate on the source document if any screening laboratory values exclude the subject from participating in the study (e.g., serum creatinine > 1.3 mg/dL).

*conduct only at Screening (Day -7 to Day -1) and Visit 8/Exit (Day 90±3).

Urinalysis

The following is a list of the minimum urine parameters that will be measured. Other additional urine parameters may also be reported.

Urinalysis
PH
Protein
Erythrocytes
Ketones
Glucose

Prior to enrolling a subject, the Clinical Investigator will indicate on the source document if any screening laboratory values exclude the subject from participating in the study.

21.4.15. Procedure for Immunogenicity Serum Sample

Approximately 5 mL of serum sample will be collected for immunogenicity analysis from the subject at Visit 1 (Day 1) and Visit 5 (Day 30±2).

Refer to the separate procedure manual for sample handling, storage, and shipment.

21.4.16. Procedure for Biomarker Serum Sample

Approximately 10 mL of blood sample will be collected for biomarker analysis from the subject at Visit 1 (Day 1), Visit 2 (Day 2), Visit 3 (Day 8±1), Visit 5 (Day 30±2) and Visit 8 (Day 90±3).

There will be up to 5 blood draws for Biomarker. The total amount of blood collected from each subject in Cohort 3 and Cohort 4 during this study will be approximately 50 mL.

Refer to the separate procedure manual for sample handling, storage, and shipment.

Table 6: Protocol Amendment 03 Summary of Changes

Page	Section Number and Title	Description of Change
4-8	2.SYNOPSIS	Modifications were made to reflect the study period and the study design changes made throughout the protocol.
16	5. INTRODUCTION	
Rationale: To update the status of the study.
 
Amendment 02 text: (None)
 
Amendment 03 text: As of June 2016, 2 subjects in Cohort 1 have been enrolled and completed the study with no adverse events, and no safety and tolerability concerns.

19	7.1. Overall Study Design and Plan.	
Rationale: To allow the cohort transition from Cohort 1 to Cohort 2 with 2 subjects safety data at least, according to the updated study status.
 
Amendment 02 context: Three subjects will be enrolled in Cohort 1. Three subjects safety data is required to make a decision by Safety Review Team whether or not the transition to Cohort 2 is acceptable.
 
Amendment 03 context: Two or Three subjects will be enrolled in Cohort 1. Two subjects safety data at least is required to make a decision by Safety Review Team whether or not the transition to Cohort 2 is acceptable.

20	Figure 1: Study Schematic	
Rationale: Updated in accordance with the change of overall study design and plan.

21	7.2. Number of Subjects	
Rationale: In accordance with the change of overall study design and plan and change of number of sites.
 
Amendment 02 text: Approximately 12 subjects (3 subjects per cohort) with refractory exudative age related macular degeneration will be enrolled at 3-4 sites. Amendment 03 text: Approximately 12 subjects (2 or 3 subjects in Cohort 1, 3 subjects each in Cohorts 2, 3 and 4) with refractory exudative age related macular degeneration will be enrolled at 5 sites.

22	7.4. Dose Adjustment Criteria	
Rationale: In accordance with the change of overall study design.
 
Amendment 02 text: When all subjects in the cohort have completed Visit 5 (Day 30±2), the Safety Review Team will again evaluate the safety parameters.
 
Amendment 03 text: When the first 2 or 3 subjects in Cohort 1 and 3 subjects in other Cohorts have completed Visit 5 (Day 30±2), the Safety Review Team will again evaluate the safety parameters.

Table 6: Protocol Amendment 03 Summary of Changes (Continued)

Page	Section Number and Title	Description of Change
24	Table 4: Schedule of Events	Rationale: Updated in accordance with the addition of blood sample collection for biomarker analysis.
25 27 27 29 31	7.6.2.1. Visit 1 (Day 1) 7.6.2.2. Visit 2 (Day 2) 7.6.2.3. Visit 3 (Day 8±1) 7.6.2.5. Visit 5 (Day 30±2) 7.6.3.1. Visit 8/Exit (Day 90±3)	Rationale: To add blood sample collection for biomarker analysis. Amendment 02 text: (None) Amendment 03 text: Biomarker serum sample (in Cohorts 3 and 4)
33	8.1. Subjects Inclusion Criteria	Rationale: To expand the subjects enrollment according to the updated status of the study in which no safety issue was seen so far. Amendment 02 text: 8.BCVA of 50 to 20 ETDRS letters (20/100 to 20/400) in the study eye. Amendment 03 text: 8.BCVA of 65 to 20 ETDRS letters (20/50 to 20/400) in the study eye.
51	13. OTHER ASSESSMENTS	Rationale: To add biomarker analysis. Amendment 02 text: 13.3 Other Assessments Other assessments include concomitant medications and exposure to study drug. Amendment 03 text: 13.3 Biomarker For the biomarker finding, serum samples will be collected according examination schedule from the subjects in Cohorts 3 and 4, and measured for levels of endoglin-related proteins. The remaining serum samples will be stored for future exploratory research to identify possible other biomarkers associated with the study drug(s) and/or ophthalmologic disease conditions. 13.4 Other Assessments Other assessments include concomitant medications and exposure to study drug.

Table 6: Protocol Amendment 03 Summary of Changes (Continued)

Page	Section Number and Title	Description of Change
52	14.1.2. Sample Size	
Rationale: In accordance with the change of overall study design and plan and change of number or sites.
 
Amendment 02 text: Approximately 12 subjects (3 subjects per cohort) with refractory exudative age related macular degeneration will be enrolled at 3-4 sites.
 
Amendment 03 text: Approximately twelve subjects (2 or 3 subjects in Cohort 1; 3 subjects in Cohorts 2, 3, and 4) with refractory exudative age related macular degeneration will be enrolled at 5 sites.

54	14.8.2. Biomarker Analysis	
Rationale: To add biomarker analysis.
 
Amendment 02 text: (None)
 
Amendment 03 text: Changes from baseline in levels of biomarkers will be summarized descriptively by dose level of DE-122.

81	24.1.16. Procedure for Biomarker Serum Sample	
Rationale: To add biomarker analysis.
 
Amendment 02 text: (None)
 
Amendment 03 text: Approximately 10 mL of blood sample will be collected for biomarker analysis from the subject at Visit 1 (Day 1), Visit 2 (Day 2), Visit 3 (Day 8±1), Visit 5 (Day 30±2) and Visit 8 (Day 90±3). There will be up to approximately 5 blood draws for Biomarker. The total amount of blood collected from each subject in Cohort 3 and Cohort 4 during this study will be up to approximately 50 mL. Refer to the separate procedure manual for sample handling, storage, and shipment.

SOC	system organ classification
US	United States
WHO-DDE	World Health Organization Drug Dictionary Enhanced

1. INTRODUCTION

This statistical analysis plan (SAP) specifies the statistical methods to be implemented for the analysis of data collected within the scope of Santen's Protocol 36-001, "A Phase I/II, Open-label, Dose-escalating, Sequential-cohort Study Assessing the Safety, Tolerability, Immunogenicity, and Bioactivity of a Single Intravitreal Injection of DE-122 Injectable Solution for the Treatment of Refractory Exudative Age-related Macular Degeneration- PAVE Study". It applies to the study protocol dated 30 June 2016 and provides detailed instructions as to how each analysis will be performed.

Results obtained from the analyses specified in the final approved version of the SAP will become the basis of the clinical study report (CSR) for this protocol. Any deviations from the final approved version of the SAP must be substantiated by sound statistical reasoning and documented in the CSR.

2. STUDY OBJECTIVE

2.1. Primary Objective and Endpoints

The primary objective is:

- To assess the safety and tolerability of a single intravitreal injection of four dose levels of DE-122 (0.5 mg/eye, 1.0 mg/eye, 2.0 mg/eye and 4.0 mg/eye) in subjects with refractory exudative age related macular degeneration.

The safety and tolerability of DE-122 will be assessed by

- adverse events (AEs)
- indirect ophthalmoscopy
- best-corrected visual acuity (BCVA)
- slit-lamp biomicroscopy
- intraocular pressure (IOP)
- fundus photography
- fluorescein angiography
- serum chemistry
- hematology
- urinalysis
- physical exam
- electrocardiogram (EKG)
- pregnancy test
- vital signs

Section 4.3.2 gives a detailed description of the safety measures to be collected in this study.

2.2. Secondary Objective and Endpoints

The secondary objective is to evaluate the bioactivity of four dose levels of DE-122 in subjects with refractory exudative age-related macular degeneration.

The bioactivity of DE-122 on resolution of fluid will be assessed using the change in CST based on SD-OCT at each visit post DE-122 treatment as compared to baseline (change in response to anti-VEGF treatment given before Visit 1 (Day 1)).

3. STUDY DESIGN

3.1. General Study Design

This is an open-label, dose-escalating, sequential-cohort study assessing the safety, tolerability, immunogenicity, and bioactivity of a single intravitreal injection of 0.5 mg, 1.0 mg, 2.0 mg and 4.0 mg DE-122 administered in approximately 12 subjects with refractory exudative age-related macular degeneration (AMD). It employs a dose-escalation design to study four cohorts of subjects as shown in the Study Design Diagram ([Figure 1](#)).

Four cohorts of subjects each will receive a single intravitreal injection of DE-122 in the study eye. Decisions regarding dose escalation in the next cohort will be based on the recommendations of the Safety Review Team consisting of an external Retina Specialist, the Medical Monitor, and the Drug Safety specialist. Dose-Limiting Toxicity response observed in any cohort will result in termination of the dose escalation.

3.2. Randomization and Masking

This is an open-label cohort study. Randomization is not employed in this study due to the dose-escalation design.

3.3. Sample Size Planning

Approximately 12 subjects (2 or 3 subjects in Cohort 1; 3 subjects in Cohorts 2, 3, and 4) with refractory exudative age related macular degeneration will be enrolled at 5 sites. The final number of subjects enrolled may be adjusted based on the presence of dose limiting toxicities

This sample size is not planned based on statistical considerations.

3.4. Visits and Assessments

Assessments at each visit and visit windows are specified in the Schedule of Event ([Table 1](#)).

Figure 1: Study Design Diagram

[figure not shown]

Table 1: Schedule of Events

Visit Number	Visit 0 (SCRN)	Visit 1		Visit 2	Visit 3	Visit 4	Visit 5	Visit 6	Visit 7	Visit 8 /Exit
Visit Schedule (Time window; days)	D-7 to -1	D1		D2	D8 (±1)	D15 (±2)	D30 (±2)	D45 (±3)	D60 (±3)	D90 (±3)
		Pre	Post							
Informed consent ^a	X									
Demographics/Eligibility	X	X								
Medical/surgical history, Concomitant medication	X	X		X	X	X	X	X	X	X
Physical exam	X									X
Vital signs	X	X		X	X	X	X	X	X	X
EKG	X				X		X			X
BCVA (ETDRS)	X	X		X	X	X	X	X	X	X
Slit-lamp biomicroscopy ^b	X	X	X	X	X	X	X	X	X	X
Intraocular pressure ^c	X	X	X	X	X	X	X	X	X	X
Indirect ophthalmoscopy ^b	X	X	X	X	X	X	X	X	X	X
SD-OCT	X	X		X	X	X	X	X	X	X
Fundus photography	X						X		X	X
Fluorescein angiography	X						X		X	X
Urine pregnancy test ^d							X		X	
Urinalysis ^e	X				X		X			X
Serum pregnancy test ^d	X									X
Hematology, chemistry serum sample ^e	X				X		X			X
Immunogenicity serum sample		X					X			
Biomarker serum sample ^f		X		X	X		X			X
DE-122 IVT Injection		X								
Rescue with anti-VEGF Injection ^g					(X)				(X)	
Anti-VEGF Injection ^h							X			
Adverse events		X	X	X	X	X	X	X	X	X

- Informed Consent Form - obtain prior to conducting any study-related activities.
- Slit-lamp biomicroscopy and indirect ophthalmoscopy will be performed prior to DE-122 or anti-VEGF intravitreal injection and within 30 minutes after injection.
- IOP will be performed before DE-122 or anti-VEGF Intravitreal injection and 40±10 minutes after injection. If IOP is increased ≥ 10 mmHg, repeat IOP measurement 60±10 minutes after the injection.
- Serum and urine pregnancy tests are to be performed on all women of child-bearing potential.
- Collect fasting urine and blood specimen.
- Biomarker serum sample will be collected from the subjects in Cohorts 3 and 4.
- If subjects meet the following rescue criteria at Visit 3 (Day 8±1) and/or at Visit 7 (Day 60±3): <5 letters gained from baseline BCVA or < 50 microns reduction from baseline CST as measured by SD-OCT.
- Subjects who do not receive rescue therapy with anti-VEGF medication at Visit 3 (Day 8±1) will receive anti-VEGF treatment at Visit 5 (Day 30±2).

4. DEFINITIONS

4.1. Time-Related Terms

4.1.1. Baseline Visit

For this study, the *baseline visit* is the Day 1 visit when the injection of DE-122 is scheduled.

4.1.2. Study Day

The *study day* variable describes the relative day of the observation starting with the reference date as Day 1. In this study, the initial injection date (visit 1 data) of the study medication is the reference day and the study day will be calculated as:

- For days prior to the injection date, Study Day = Date – Injection Date
- For days on/after the injection date, Study Day = Date – Injection Date + 1

Note that there is no Study Day 0.

4.1.3. Out-of-Window Measurements and Analysis Window

A measurement collected at a visit is an *out-of-window* measurement if the study day of the visit falls outside of a visit window specified in [Table 1](#), or a *within-window* measurement otherwise.

If there are many *out-of-window* measurements for a visit, then a window wider than the specified visit window may be defined for analysis purposes to minimize missing data. Such wider windows for analysis (i.e., *analysis windows*), if needed, will be determined by the Medical Monitor and the Study Statistician based on the review of all *out-of-window* measurements before the database lock.

For analyses involving post-baseline visits, if there are two or more measurements that fall into the same analysis window of a post-baseline visit, then the measurement closest to the target assessment day will be selected for that visit. In the case that two measurements are closest and equidistant to the target assessment day, i.e., one is before and one is after the target assessment day, the later one will be selected for that visit.

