7.6.2.5. Visit 5 (Day 30±2)

- The following assessments must be performed prior to administration of anti-VEGF medication
 - Query for AEs
 - Update medical history and medications
 - Vital signs
 - EKG
 - BCVA (ETDRS)
 - Slit-lamp biomicroscopy
 - IOP
 - Indirect ophthalmoscopy
 - SD-OCT
 - Fundus photography
 - Fluorescein angiography
 - Urinalysis
 - Urine pregnancy test
 - Hematology, chemistry serum sample
 - Immunogenicity serum sample
 - Biomarker serum sample (in Cohorts 3 and 4)
- Upload all collected images (SD-OCT, fundus photograph and fluorescein angiogram) to sponsor.
- Subjects who did not receive rescue therapy with anti-VEGF medication at Visit 3 (Day 8±1) will receive anti-VEGF treatment. The anti-VEGF medication should be performed using the same drug received just prior to enrollment in the study ([Section 9.2.3](#)). If the subject received rescue therapy at Visit 3 (Day 8±1), anti-VEGF treatment and post-injection assessments are not necessary.
- The following assessments must be performed after the administration of anti-VEGF treatment:

- Within 30 minutes following anti-VEGF treatment
 - Slit-lamp biomicroscopy
 - Indirect ophthalmoscopy
- IOP: 40 (± 10) minutes following injection
 - If post-injection IOP is increased ≥ 10 mmHg from pre-injection IOP, the IOP will be measured again 60 (± 10) minutes following injection. If there is an increase of ≥ 10 mmHg at 60 (± 10) minutes post-injection compared to pre-injection IOP, the subject should be prescribed a topical IOP-lowering medication and monitored for resolution of the event by the Clinical Investigator. An IOP increase of ≥ 10 mmHg shall be reported as an AE.
- AE assessments must be performed after the anti-VEGF treatment.
- Schedule the subject to return for Visit 6 (Day 45 \pm 3).

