9.2.1. Prohibited Medications or Treatments

Any treatments for exudative AMD in the study eye other than DE-122 are prohibited during the study, except anti-VEGF treatment as a rescue therapy at Visit 3 (Day 8±1) and/or at Visit 7 (Day 60 ±3), and anti-VEGF treatment at Visit 5 (Day 30±2) as described in [Section 9.2.2](#) and [Section 9.2.3](#).

Any systemic treatments with anti-VEGF agents (e.g., bevacizumab) are prohibited during the study.

The decision to administer a prohibited concomitant medication or treatment during the study should be made with the safety of the subject as the primary consideration. Whenever possible, Santen should be notified before any prohibited medication or treatment is administered or if the permissibility of a specific medication or treatment is in question.

9.2.2. Rescue Therapy at Visit 3 (Day 8±1) and/or at Visit 7 (Day 60±3)

Rescue therapy is defined as IVT injection of anti-VEGF medication which is the same medication administered just prior to the enrollment in the study. Rescue therapy with anti-VEGF medication may be allowed at Visit 3 (Day 8±1) and/or at Visit 7 (Day 60±3) provided the following rescue criteria are met: < 5 letters gained from baseline BCVA or < 50 microns reduction from baseline CST as measured by SD-OCT.

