9.2.3. Anti-VEGF treatment at Visit 5 (Day 30±2)

Subjects who did not receive rescue therapy with anti-VEGF medication at Visit 3 (Day 8±1) will receive anti-VEGF treatment at Visit 5 (Day 30±2). The anti-VEGF injection should be performed using the same anti-VEGF medication administered just prior to the enrollment in the study.

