11.2.6. Intraocular Pressure

IOP will be measured by applanation tonometry and reported in millimeters of mercury (mmHg) at each study visit. On the visit of DE-122 or anti-VEGF injection, IOP will be measured before DE-122 or anti-VEGF injection and 40 (±10) minutes after injection. If post-injection IOP is increased ≥ 10 mmHg from pre-injection IOP, the IOP will be measured again 60 (±10) minutes following injection. If there is an increase of ≥ 10 mmHg at 60 (±10) minutes post-injection compared to pre-injection IOP, the subject will be prescribed a topical IOP-lowering medication until he or she returns for follow-up per the Clinical Investigator's discretion (an unscheduled visit may apply), and the IOP increase of ≥ 10 mmHg shall be reported as an AE.

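### The by-visit selection rule in SAP 4.1.3 ignores anti-VEGF timing, so in an uncommon sequence of events an unscheduled post-injection reading replaces the pre-injection value

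*SAP*

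**What the plan says.** SAP Section 4.1.3 gives one rule for choosing a by-visit value. It applies "if there are two or more measurements that fall into the same analysis window of a post-baseline visit", and then "the measurement closest to the target assessment day will be selected for that visit". Ties are settled where "one is before and one is after the target assessment day, the later one will be selected for that visit". Distance from the target day is the only criterion. The section mentions neither anti-VEGF injections nor the difference between scheduled and unscheduled readings. It also lets the windows be widened before database lock and sets no limits on this.

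The SAP restricts values to pre-injection readings only in Sections 4.2.3 and 4.2.4, and both concern the DE-122 injection at Baseline. Section 4.1.4 leaves analysis visit and analysis time point to the ADaM specifications.

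Under the Protocol, anti-VEGF may be given as rescue at Visits 3 and 7 (Section 9.2.2). It is given at Visit 5 to subjects who were not rescued at Visit 3 (Section 9.2.3). For Visit 5, Section 7.6.2.5 says: "The following assessments must be performed prior to administration of anti-VEGF medication". Slit-lamp, IOP and ophthalmoscopy readings are taken both before and after every injection (Sections 11.2.5 to 11.2.7). At Visits 3 and 7 the visit's own BCVA and CST decide whether rescue is allowed, so by implication they come before it. Section 7.6.4 allows study procedures to be repeated at unscheduled visits. After a post-injection IOP rise, Section 11.2.6 notes that "an unscheduled visit may apply".

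**The concern.** The protocol fixes the order of measurement and injection within a visit, but the SAP's selection rule does not preserve that order across days. A scheduled reading taken before the target day can lose to an unscheduled reading a day or more later, after anti-VEGF has been given.

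SAP Section 2.2 defines bioactivity as the change in CST at each visit after DE-122, and SAP Sections 8 and 9 summarize BCVA, IOP, CST and macular volume by analysis visit. For a rescued subject at Visit 3, or a subject at Visit 5 who was not rescued earlier, the swapped value would combine DE-122 with anti-VEGF and appear in the table as the response to DE-122. Protocol Section 14.6 also promises the change in retinal thickness after anti-VEGF injection, which needs the pre-injection value as its starting point. That need applies at Visit 7 as well.

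**Working it through.** The plan states no figure on this point, so there is none to reproduce. The check applies the rule literally.

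**Inputs.** Windows from the schedule of events: Visit 3, Days 7–9, target 8; Visit 5, Days 28–32, target 30; Visit 7, Days 57–63, target 60. Cohort sizes from SAP Section 3.3: 2 or 3 subjects in Cohort 1, and 3 in each of Cohorts 2 to 4.

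**Set-up.** Let t be the target day, d the scheduled visit (pre-injection reading, anti-VEGF given that day) and u > d a later unscheduled reading in the same window. The rule selects u when |u − t| ≤ |d − t|.

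- If d is on or after t, u is always further away, so no swap occurs.
- If d = t − k, the rule selects u on any day from t − k + 1 to t + k, which is 2k days. One of these, u = t + k, wins through the tie clause.
- For a window of ±w days, the number of (d, u) pairs is (2w + 1)(2w)/2. The number swapped is the sum of 2k for k = 1 to w, which is w(w + 1), and w of these are ties.
- If the unscheduled reading comes 1 or 2 days after the visit, every scheduled day before target is exposed: w of 2w + 1 days.

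| Visit | w | Scheduled days exposed (re-reading 1–2 days later) | Pairs swapped | Of which ties |
|---|---|---|---|---|
| 3 | 1 | Day 7: 1 of 3 | 2 of 3 | 1 |
| 5 | 2 | Days 28–29: 2 of 5 | 6 of 10 | 2 |
| 7 | 3 | Days 57–59: 3 of 7 | 12 of 21 | 3 |

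Example: Visit 5 and its injection fall on Day 28, with a recheck on Day 30. The rule drops Day 28 and reports Day 30. These counts assume that an injection and an in-window re-reading have both happened. They are not probabilities.

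**Widened windows.** The SAP gives no limits, so assume windows running to the midpoints between visits (Days 5–11, 23–37 and 53–75). The swapped pairs become 12 of 21, 56 of 105 and 56 of 253. More combinations are exposed, though they are a smaller share of all pairs.

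**Who is exposed.**

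- Visit 3: rescued subjects only.
- Visit 5: only subjects not rescued at Visit 3. The others get no injection at Visit 5, and their Day 30 values already follow anti-VEGF.
- Visit 7: subjects rescued there. Everyone following the schedule has had anti-VEGF at Visit 3 or Visit 5 by then.

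**Effect on a mean.** Shift = (post-injection value − pre-injection value)/n, so the weight is 1/3 (33%) with n = 3 and 1/2 (50%) with n = 2.

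- IOP, assuming the recheck is 10 mmHg above the pre-injection value: 10/3 = 3.3 mmHg, or 10/2 = 5 mmHg. The true difference could be smaller or have the opposite sign, since topical IOP-lowering medication may have been prescribed.
- CST, assuming a fall of 50 to 150 microns: 50/3 = 16.7 to 150/3 = 50 microns, or 50/2 = 25 to 150/2 = 75 microns. The documents give no anti-VEGF effect over a few days, and it may be smaller.

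**After the fix.** With selection limited to readings before that visit's injection, the swapped pairs in the protocol windows are 0 of 3, 0 of 10 and 0 of 21.

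**The case against.** Four arguments count against the point.

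1. Read strictly, an analysis window is a widened window set only if needed, so the rule might not operate in the protocol windows. The wording allows that reading. But the SAP then has no rule for multiple readings in the protocol windows, and the problem remains in any widened window.
2. Unscheduled data go on a separate form, and SAP 4.1.3 never says that they are pooled with scheduled data. However, each protocol window holds only one scheduled visit, and distance from target cannot separate same-day repeats. The rule has something to choose between only if unscheduled readings enter.
3. The ADaM specifications could settle the matter. They could, but SAP 4.1.4 states no anti-VEGF condition for them to carry out.
4. The study is small and descriptive with no hypothesis (Protocol Section 14.1.3), and all parameters are listed, so a swap could be found in the listings. This stands, and it keeps the point minor.

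Some stronger readings are tempting but not supported. A reader might take 1/3, 2/5 and 3/7 as the chance of a swap, but they are conditional day counts. A reader might infer that Visit 7 would otherwise show DE-122 alone, but values there already follow earlier anti-VEGF. A reader might expect CST to be the measure at risk, but the one unscheduled visit that the protocol foresees follows an IOP rise, and nothing makes BCVA or SD-OCT part of it. Finally, a reader might suppose that SAP 4.1.4 already separates same-day pre- and post-injection readings. It defines neither variable, and the tie clause, which describes one reading on each side of the target day, does not cover same-day readings.

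**Conclusion.** The point holds as a minor flaw in a stated rule. Followed as written, SAP 4.1.3 can discard the pre-injection value that the Protocol requires at Visit 5 and implies at Visit 3, and report a value affected by anti-VEGF as the DE-122 response. At Visit 7 it only loses that visit's pre-injection value.

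Three things must coincide: a scheduled visit before the target day, an anti-VEGF injection at that visit, and an unscheduled re-reading of the same measure that is in the window and at least as close to target. The documents give no frequency for this, and it should be uncommon. IOP is the likeliest measure affected; BCVA or CST is affected only if repeated.

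If a swap happens, one value carries 1/3 of a cohort mean, or 1/2 if Cohort 1 has two subjects. The micron and mmHg shifts above rest on assumed differences. That the Visit 5 order is meant to isolate DE-122 is inferred from the bioactivity definition; the Protocol does not state the reason.

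**What to change.** Add to SAP 4.1.3: for by-visit summaries and change from baseline at any visit where anti-VEGF is given, the analysis value is the scheduled pre-injection measurement. If that is missing, it is the closest in-window measurement taken before that injection. The same limit applies in any widened window.

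State alongside it that the protocol-required same-day post-injection slit-lamp, ophthalmoscopy and IOP readings stay assigned to that visit under a separate post-injection time point. Unscheduled post-injection readings stay in the listings, including the SAP 8.4 listing of IOP increases of at least 10 mmHg. A blanket ban on assigning post-injection readings to the visit would be wrong, because it would leave the required safety readings without a visit.

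The cost is a few sentences in the SAP and a matching ADaM derivation. No study procedure changes. The downside is an occasional analysis value further from the target day, or one left missing.
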